4.5. Removal of Patients

In accordance with the Declaration of Helsinki, patients have the right to withdraw from the study at any time for any reason. The Investigator and Sponsor also have the right to withdraw patients from the study. Patients may be removed from the study for the following reasons:

- Adverse reactions
- Clinical sepsis regardless of the cause
- At the request of the Investigator, MM, DSMB or Sponsor, whether for administrative or other reasons
- Protocol violation or unreliable behavior
- Termination of the study by the Sponsor

The date of and the reason for discontinuation will be recorded in the electronic case report form (eCRF).

Patients who withdraw from the study after receiving the first dose of IMP for reasons other than safety or tolerability may be replaced:

- Patients who withdraw before the Day 180 follow-up visit (primary end point) may be replaced upon consultation with the coordinating investigator and sponsor
- Patients who withdraw after the Day 180 follow-up visit will not be replaced

If a patient discontinues, all end of study visit procedures should be conducted.

If a patient is removed from the study, the date of the last dose of IMP and all observations collected up to the time of termination will be recorded on the eCRF along with the reason for termination. Scheduled safety evaluations and follow-up examinations (see Visit Schedule, Appendix A) will be conducted, if possible.

When a patient fails to return for scheduled assessments, the following efforts should at a minimum be made to contact him/her to determine a reason for the failure to return: 3 phone attempts, including the date and time, should be documented in the patient's source documents. If there is no response to the phone calls, a certified letter should be sent to the patient. After these efforts have been exhausted, a patient should be identified as lost to follow-up in the eCRF.

Patients enrolled into the Combination Cohorts who are excluded prior to receiving the first dose of IMP (teplizumab and AG019 or corresponding placebos) due to any of the criteria mentioned in Section 11.4.3.5 will be replaced. Replacement of patients will be done through the IRT. Details of this procedure are outlined in the IRT manual.

Confidentiality Statement

4.6. Special considerations

As this is a First In Human study, no participating patient is allowed to donate any sperm or egg cells during their participation in the study and for 12 months thereafter.

5. STUDY TREATMENT

5.1.Treatments

5.1.1AG019

Single dose patients will be treated with (2 or 6 capsules of) AG019.

All patients in the repeat dose cohorts, and all patients in the combination cohorts who are randomized to study treatment, will be treated for 8 weeks with AG019 with one of the doses listed in Table 2:

Table 2: AG019 dosing regimens for repeat dose patients

Dose	Number of capsules	Total daily dose	Treatment duration
Low dose AG019	2 (1 morning, 1 evening)	XXX	8 weeks
High dose AG019	6 (3 morning, 3 evening)	xxx	8 weeks

The total treatment duration for repeat dose patients is 8 weeks or 56 days. Patients will be required to take AG019 for 56 days, even if the Day 56 follow-up visit is not scheduled on Day 56 (there is a 2-day visit window on the Day 56 follow-up visit).

- If the Day 56 follow-up visit is scheduled on Day 54 or Day 55, patients will take their remaining AG019 home again and will continue to take AG019 until the evening dose on Day 56. The patients will then take their remaining AG019 back to the site on Day 90 for final accountability
- If the Day 56 follow-up visit is scheduled on Day 57 or Day 58, patients should be instructed to take AG019 until the evening dose on Day 56.

The daily dose of AG019 to be used in the Phase 2a portion of the study (combination cohorts) is not yet known and will be determined by the results of the Phase 1b portion of the study (AG019 cohorts). Based upon the data obtained in the nonclinical studies, the Sponsor anticipates that a 6-capsule regimen will be administered in the combination cohorts. Following rules will apply:

If the DSMB concludes that no safety concerns are associated with the high dose of AG019 (6 capsules per day) in the Phase 1b portion of the study (AG019 cohorts), the patients enrolled

Confidentiality Statement

in the Phase 2a portion of the study (combination cohorts) will take the high dose of AG019 for 8 weeks.

If the DSMB concludes that safety concerns are associated with the high dose of AG019 (6 capsules per day) in the Phase 1b portion of the study (AG019 cohorts) and that no safety concerns are associated with the low dose of AG019 (2 capsules per day), the DSMB will recommend lowering the AG019 dose in all ongoing and planned (AG019 and) combination cohorts.

If, at any time during the study, safety concerns associated with the high dose of AG019 are identified, the DSMB will recommend lowering the daily dose of AG019 in all ongoing and planned AG019 cohorts, as well as in all ongoing and planned combination cohorts.

XXX

5.1.2Teplizumab

All patients in the combination cohorts who are randomized to study treatment, as well as the first 2 patients in the combination cohorts who are treated in open label, will be treated for 12 days with teplizumab (daily IV infusions) according to the below schedule, in addition to their AG019 treatment:

XXX			

XXX

The parameters used to calculate the daily dosing of study drug will be based on the height and weight at Day 1. The total cumulative average dose will be 9034 μ g/m² or approximately ~17 mg for each patient. This total dose is the same as that used in previous trials in a 14 day regimen (Sherry et al., 2011; Hagopian et al., 2013; Herold et al., 2013; Herold et al., 2013) with the change that the protocol

Confidentiality Statement

has been shortened XXX

5.1.3T1D therapy during the study

During the study, all patients will receive appropriate diabetic therapy according to current ADA or equivalent guidelines. Treatment with commercially available insulin (multiple dose insulin injection therapy, continuous subcutaneous insulin infusion therapy or analogue therapies) is allowed. Treatment with other forms of commercially available insulin therapy, or treatment with experimental insulin, is not allowed during this study.

In accordance with ADA recommendations, preprandial glucose level target should be 4.4-7.2 mmol/L (80-130 mg/dL) and peak post prandial (1-2h after meal) glucose level target should be <10 mmol/L (<180 mg/dL).

5.1.40ther concomitant therapy

Any concomitant therapy used by the patient at any time following ICF signature must be recorded in the eCRF through the end of the short term follow-up must be recorded on the eCRF. In addition, for any SAEs that require medication for treatment, those medications must be recorded on the concomitant medications page. The medication name, dosage, frequency, route of administration, start and stop dates, and indication for use must be recorded. The medical monitor should be notified in advance of (or as soon as possible after) any instances in which prohibited therapies are administered. The MM will subsequently advise on actions to be taken, if any.

Prohibited therapy during the entire treatment period includes any antibiotic treatment known to affect the viability of L. lactis sAGX0407 (see Appendix B), β -cell stimulants, immunosuppressive or immunomodulatory therapies, including systemic steroids, other investigational drug(s), vaccination with live virus or organism, anti-CD3 antibody, any anti-diabetic agents other than insulin, medications known to influence glucose tolerance and daily use of non-steroidal anti-inflammatory agents.

For patients enrolled in the combination cohorts, premedication with ibuprofen or similar non-steroidal anti-inflammatory drugs (NSAID) and with an antihistamine is recommended and may be useful in patients who develop rashes during teplizumab administration.

As paracetamol may induce false positive signals of hyperglycemia by the continuous glucose monitoring devices, its use for reasons other than the reasons mentioned in the previous paragraph should be avoided as much as possible throughout the study.

Confidentiality Statement

5.2. Description of the cohorts

The enrollment plan is presented in Figure 1 and is described below.

5.2.1AG019 Cohorts

A total of 8 single dose patients and up to 24 repeat dose patients⁸ will be enrolled sequentially into the following AG019 cohorts:

- AG019 Cohort 1: 2 capsules per day, patients 18-40y
 - Single dose: 2 patients
 - Repeat dose: up to 6 patients⁸
- AG019 Cohort 2: 6 capsules per day, patients 18-40y
 - Single dose: 2 patients
 - Repeat dose: up to 6 patients⁸
- AG019 Cohort 3: 2 capsules per day, patients 12-17y
 - o Single dose: 2 patients
 - Repeat dose: up to 6 patients⁸
- AG019 Cohort 4: 6 capsules per day, patients 12-17y
 - o Single dose: 2 patients
 - Repeat dose: up to 6 patients⁸

A total of 2 single dose patients and up to 6 repeat dose patients⁸ will be enrolled in each open label safety cohort, designed to investigate the safety profile of AG019 administered alone.

Single dose patients

In a first stage, 2 single dose patients will be enrolled in a staggered way. Each of these patients will be treated for 1 day with AG019 (number of capsules of AG019 will correspond to the cohort these patients have been enrolled into). These patients will be followed up for a total of 4 days (Treatment day [Day 1] plus 3 additional days), after which they will have completed their study participation (Day 4).

After study completion of each single dose patient, the treating Investigator and MM will review the collected data, and if no safety concerns are identified, treatment of the next patient (i.e., the second single dose patient or the first repeat dose patient) can begin.

Each single dose patient will be offered the option of being re-enrolled as repeat dose patient, provided that no safety concerns have been identified during their participation as a single dose patient. A wash-

Confidentiality Statement

This document contains confidential information. It is intended solely for the use of the principal investigator, coinvestigators, staff, appropriate institutional review boards or ethical committees, and other required regulatory bodies.

AG019-T1D-101 CSP Final 9.0 11-Jun-2020

⁸ 4 repeat dose patients will be enrolled per AG019 cohort. In addition, both single dose patients in each AG019 cohort will be offered the option of being re-enrolled as repeat dose patients, provided that no safety concerns have been identified during their participation as a single dose patient. Therefore, if both single dose patients agree to be re-enrolled as repeat dose patients, the maximum number of repeat dose patients per cohort will be 6.

out period of 7 days will be required before the single-dose patients can be re-enrolled as repeat dose patients, to ensure that no AG019 bacteria are present in their GI tract at the time of re-enrollment. In addition, these patients cannot be enrolled as staggered patients into the repeat dose group.

If a single dose patient wishes to be re-enrolled as repeat dose patient, all inclusion and exclusion criteria applicable to repeat dose patients should be met (including those criteria that do not apply to single dose patients).

Repeat dose patients

A minimum of 4 repeat dose patients will be enrolled per AG019 cohort. In addition, both single dose patients in each AG019 cohort will be offered the option of being re-enrolled as repeat dose patients in the same AG19 cohort, provided that no safety concerns have been identified during their participation as a single dose patient. Therefore, if both single dose patients agree to be re-enrolled as repeat dose patients, the maximum number of repeat dose patients will be 6.

Each of these repeat dose patients will be treated daily for 8 weeks with AG019. The first 2 repeat dose patients will be enrolled in a staggered way.

- After treatment of the first patient, the data collected up to the Day 7 follow-up visit will be reviewed by the treating Investigator and MM, and if no concerns are identified, the second patient will be treated.
- After the Day 7 follow-up visit of this second patient, the collected data will be reviewed by the treating Investigator and MM, and if no concerns are identified, the remaining patients will be treated.

Once all repeat dose patients in a cohort have had their Day 7 follow-up visit, the DSMB will review all available data from all enrolled patients in all cohorts. If no safety concerns are identified, the DSMB will formulate a recommendation to the sponsor on opening the next cohort(s) for treatment, according to the enrollment schedule outlined in Figure 1. Detailed guidelines on the recommendations to be formulated by the DSMB will be described in the DSMB Charter. A brief summary of these guidelines is included in Section 11.4.2.

All Repeat dose patients in all AG019 cohorts will be followed up for a total of 12 months (8 weeks of treatment plus 10 months of post-treatment follow-up). After the 12-month follow-up visit (Day 360) the patients will have completed their participation in the study.

5.2.2Combination Cohorts

The Phase 2a double-blind portion of the study will evaluate 2 cohorts ("combination cohorts") of 12 patients. Each patient will be administered 6 capsules daily 9 of AG019 (or placebo) for 8 weeks, in association with daily IV infusions of teplizumab for the first 12 days of the 8-week treatment period.

Confidentiality Statement

⁹ The dose of AG019 to be administered in the Phase 2a portion of the study is not yet known and will be determined by the results of the Phase 1b portion of the study. If the AG019 cohorts reveal safety concerns associated with the 6-capsule treatment, the DSMB will recommend lowering the AG019 dose in all AG019 and combination cohorts.

- Combination Cohort 1: 12 patients 18-40y to receive AG019 (6 capsules per day⁹, 8 weeks) plus teplizumab (daily infusions, 12 days), or matching placebo capsules and placebo infusions
- **Combination Cohort 2**: 12 patients 12-17y to receive AG019 (6 capsules per day⁹, 8 weeks) plus teplizumab (daily infusions, 12 days), or matching placebo capsules and placebo infusions

Within each of these combination cohorts, the first 2 enrolled patients will be treated with active treatment (AG019 plus teplizumab) in an open label fashion. Patients 3-12 will be randomized (4:1) to receive (double) active treatment or (double) placebo in a double-blind fashion. Therefore enrollment will be done as follows:

- Treatment of patient 1: Treatment with AG019 plus teplizumab
 - > Data review of all data collected up to the Day 12 follow up visit (the last day of teplizumab infusion) (treating Investigator and MM)
- Treatment of patient 2: Treatment with AG019 plus teplizumab
 - ➤ Data review of all data collected up to the Day 12 follow up visit (the last day of teplizumab infusion) (DSMB review of all available data from all patients in all cohorts)
- Treatment of patients 3-12: randomization (4:1) to double active treatment or double placebo.

All patients in all Combination cohorts will be followed up for a total of 12 months (8 weeks of treatment plus 10 months of post-treatment follow-up). After the 12-month follow-up visit (Day 360) the patients will have completed their participation in the study.

5.3. Identity of Investigational Medicinal Product

5.3.1AG019

The clinical formulation of AG019 DS consists of live GM *L. lactis* bacteria, genetically modified to secrete hIL-10 and hPINS. The bulk DS is a slightly yellow, lyophilized powder.

The oral IMP consists of solid, XXX capsules filled with AG019 DS and XXX.

XXX.

XXX

Confidentiality Statement

5.3.2Teplizumab

The formul	ation of teplizumal	b consists of:
XXX		

XXX

5.4. Labelling, Packaging and Storage

XXX

5.5.Investigational Medicinal Product Administration

XXX

Detailed instructions for dose preparation and dispensing to patients will be provided to the clinical site by the Sponsor or its designee.

Confidentiality Statement

Total bilirubin, AST, ALT, LDH, Complete Blood Count (CBC), and INR will be evaluated to verify the need to withhold teplizumab (or placebo) infusion prior to each (potential) teplizumab administration, as described in Appendix A. The drug infusion withholding criteria presented in Section 11.4.3.5 should be evaluated.

5.6.Placebo/Comparator

XXX

AG019 placebo and teplizumab placebo will be packaged identically to their active counterparts and will be matched for size, color and taste (as applicable), to prevent possible breaches in the blinding.

Administration of placebo will be identical to administration of its respective active treatment.

5.7. Study Drug Accountability

The Investigator or his/her designee is responsible for ensuring adequate accountability of all used and unused study drug (AG019, teplizumab and their corresponding placebos). This includes acknowledgement of receipt of each shipment of study drug (quantity and condition), patient dispensing records and returned or destroyed study drug. Dispensing records will document quantities received. Quantities dispensed to patients will be documented, including lot number, date dispensed, patient identification number, patient initials and the initials of the person dispensing the study drug.

Throughout the course of the study, the Sponsor or its designee will perform study drug accountability and provide instructions for adequate study drug disposal. Study drug accountability records must be readily available for audit by the Sponsor or its designee and for inspection by regulatory authorities at any time.

The Investigator will not allow study drug to be given to any patient not included in the study or any unauthorized person.

It is the responsibility of the site personnel to maintain adequate study drug dispensing records.

AGO19 (or corresponding placebo) compliance will be reviewed by the study staff at every follow-up visit during the active treatment period. Each patient will be instructed to return all used and unused study drug at each visit during the active treatment period and at the end of the treatment phase. A count of the used and unused capsules will be performed to assess compliance.

Teplizumab (or corresponding placebo) accountability and compliance will be verified at every follow-up visit by the site staff. Adequate documentation of receipt, dispensing and return will be maintained by the site staff.

Confidentiality Statement

5.8. Return and destruction of study drug

All patients are required to return all empty medication blisters, partially used blisters and unused blisters to the study site upon completion of treatment or in case of withdrawal. If a patient is lost to follow-up during the treatment phase, the site should make every reasonable effort to obtain the used, partially used and unused blisters.

Unused AG019 capsules will be destroyed by a dedicated drug destruction facility. Local destruction by the site is not allowed unless mandated by the site's local procedures. If unused, used and partially used study drug is destroyed on site, this can only be done after IMP accountability has been performed by the Sponsor or its designee.

Materials used for teplizumab infusions, as well as empty teplizumab vials, can be destroyed locally by the sites. All materials and vials are to be treated as hazardous medical waste per the site's Standard Operating Procedures.

Unused teplizumab vials will be destroyed by a dedicated drug destruction facility. Local destruction by the site is not allowed unless mandated by the site's local procedures. If unused, used and partially used study drug is destroyed on site, this can only be done after IMP accountability has been performed by the Sponsor or its designee.

5.9.Method of Assigning Patients to Treatment

In the AG019 cohorts, all patients (single dose and repeat dose) will be treated with AG019. Registration of every patient will be required through the IRT (see Section 4.4).

In the combination cohorts, the first 2 patients will be treated with AG019 + teplizumab. The remaining 10 patients in each combination cohort will be randomized (4:1) to study drug or placebo. Patients randomized to receive study drug will be treated with AG019 + teplizumab, patients randomized to receive placebo will be treated with AG019-placebo and teplizumab-placebo. Randomization will be done through the IRT.

During the screening and treatment phase, every study visit for every patient will need to be registered in the IRT. Details about the functionality and use of the IRT are found in the IRT manual.

5.10.Blinding

For the randomized patients in the combination cohorts, blinding will be accomplished by arranging for AG019 and placebo components as well as teplizumab and placebo components to have identical packaging. IMP will be delivered in a blinded fashion, as outlined in the Pharmacy Manual. All study personnel at the site, the patient and the Sponsor (except for the clinical supply manager) will be blinded to treatment allocation in the randomized portion of the combination cohorts for the first 6 months of the study. Once all patients in all combination cohorts have completed their 6-month follow-up visit (Day 180), unblinding will be done and all data will be analyzed and reported. After completion of the full 12 months follow-up all additional data will be analyzed and reported separately.

Confidentiality Statement

The identity of IMP assigned to patient numbers or to individual boxes of IMP can be accessed through IRT. When it is medically indicated, the Investigator may contact the MM and Sponsor to discuss the possibility of breaking the blind for a patient. A patient's treatment assignment should only be unblinded when knowledge of the treatment is essential for the further management of the patient (i.e., medical emergency). In the absence of a medical emergency, breaking the code should not be considered.

For emergency blind-break procedures, contact the MM or his/her designee at the contact numbers provided in the Study Manual. The reason and date/time of the unblinding and the name of the individual who broke the blind must be appropriately documented in the patient's medical record or source documents and in the eCRF.

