After all patients in all AG019 and Combination cohorts have completed their 6-month follow-up visit unblinding will be done and all data will be analyzed and reported. After completion of the full 12 months follow-up all additional data will be analyzed and reported separately.

More details on the analysis and presentation of study results will be provided in the statistical analysis plan (SAP). The SAP will be finalized prior to the unblinding of treatment allocation codes.

10.1.Study Endpoints

Primary Endpoint

The primary end point will be assessed by analysis of the incidence of treatment-emergent adverse events (TEAEs) collected up to the 6-month follow-up visit. A TEAE is defined as any event not present prior to the initiation of the treatment(s) or any event already present that worsens in either intensity or frequency following exposure to the treatment(s).

Secondary Endpoints

The pharmacodynamic activity of the study drug(s) will be assessed by measurement of biomarkers in blood and serum samples. Relevant parameters will be assessed, including immune markers for effect, relevant T1D parameters and relevant cytokines. Details about the analysis of the collected PD samples will be described in the SAP.

Following parameters will be assessed for analysis of systemic and local exposure to *L. lactis*:

- Presence of live L. lactis clinical strain bacteria in whole blood
- Measurable serum levels of hIL-10 and hPINS
- Presence of *L. lactis* clinical strain bacteria in fecal excretion

Safety information collected at all other time points will be assessed as secondary end points.

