10.7. Safety Analysis

Safety will be assessed based on TEAEs, physical examination findings, vital sign measurements and clinical laboratory tests.

Adverse events will be coded to a Medical Dictionary for Regulatory Activities (MedDRA) preferred term and system organ classification. The occurrence of treatment emergent AEs will be summarized by treatment frequency received using preferred terms, system organ classifications and severity. If a patient experiences multiple events that map to a single preferred term, the greatest severity and/or strongest investigator assessment of relation to study drug will be assigned to the preferred term for the appropriate summaries. Separate summaries of treatment emergent SAEs and treatment emergent AEs that are related to either IMP will be generated. Summaries may be repeated according to study phase. All AEs will be listed for individual patients showing both verbatim and preferred terms.

Descriptive summaries of vital signs and quantitative clinical laboratory changes will be presented by treatment received and study visit. The number and percentage of patients experiencing laboratory abnormalities and clinically relevant laboratory abnormalities will be summarized by treatment received. Cross tabulations of baseline abnormality vs. worst post treatment abnormality for selected laboratory assessments will presented by treatment received.

Abnormal physical examination findings will be presented by treatment received. The number and percentage of patients experiencing each abnormal physical examination finding will be included.

Prior and concomitant medications will be coded using the World Health Organization (WHO) dictionary. These data will be listed.

The number and percentage of patients with presence of sAGX0407 bacteria will be summarized by treatment group.

10.8.Interim Analysis

Interim analyses will be performed according to the below schedule:

After the last Day 180 follow-up visit of the last patient enrolled into the Phase 1b portion of
the study, a preliminary analysis of the data collected up to 6 months will be performed for
these patients.

Confidentiality Statement

- Once all patients enrolled in Combination Cohort 1, as well as the 2 patients enrolled into the
 open label portion of Combination Cohort 2, have completed the Day 180 follow-up visit,
 unblinding will be done and an interim analysis will be performed.

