- After the last Day 180 follow-up visit of the last patient enrolled into Combination Cohort 2, all patients in this cohort will be unblinded and an interim analysis will be performed on all, which will include an analysis of the primary endpoint of the study.

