6.9 Interim Analysis

Preliminary results (interim analysis 1) for the open-label part of the study and a second interim analysis (described in the Interim Analysis Plan [IAP]) has been performed previously.

The primary analysis will be performed when all patients have passed the Day 180 visit. This interim analysis will contain the same TFLs that will be produced for the final output, if possible.

All decisions on data for blinded subjects will be taken before breaking the blind for the third interim analysis. Since this is a study of descriptive nature, with no statistical tests, the influence of the interim analyses should be considered negligible.

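### Blinding of site staff and patients is promised only to Day 180 and the recipients of the interim codes are not named, while judgement-dependent secondary data are collected to Day 360

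*Protocol*

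**What the plan says.** Protocol 5.10 names the blinded parties: "All study personnel at the site, the patient and the Sponsor (except for the clinical supply manager) will be blinded to treatment allocation". The same sentence sets the limit: these parties "will be blinded to treatment allocation in the randomized portion of the combination cohorts for the first 6 months of the study". The section continues: "Once all patients in all combination cohorts have completed their 6-month follow-up visit (Day 180), unblinding will be done". Data to that point are then analysed and reported, and the remaining 12-month data are reported separately.

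The trigger is worded differently elsewhere. The introduction to Protocol Section 10 has: "After all patients in all AG019 and Combination cohorts have completed their 6-month follow-up visit unblinding will be done". Protocol 10.8 splits it by cohort. The first break comes "Once all patients enrolled in Combination Cohort 1, as well as the 2 patients enrolled into the" open-label portion of Combination Cohort 2 have reached Day 180. After the last Day 180 visit in Combination Cohort 2, "all patients in this cohort will be unblinded and an interim analysis will be performed on all".

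Follow-up does not stop there. Protocol 5.2.2 states: "All patients in all Combination cohorts will be followed up for a total of 12 months". Under 7.3.4.3 and 7.3.4.4, the Day 270 and Day 360 visits both collect adverse events, insulin use, hypoglycaemic events, CGM and HbA1c, and Day 360 adds an MMTT. Protocol 10.1 makes safety information outside the primary window a secondary endpoint.

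SAP 6.9 requires decisions on blinded subjects' data before the third break. It then argues that, with no statistical tests, "the influence of the interim analyses should be considered negligible".

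**The concern.** An interim analysis needs only the people running it to know the allocation. Here the parties whose blind expires at 6 months are the site staff, the patient and the sponsor, and nothing in either document keeps any of them blinded afterwards.

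Several of the later data depend on judgement. The investigator decides relatedness (Protocol 8.3), whether an abnormal laboratory value is an adverse event (6.2), and whether level 1 hypoglycaemia or a non-major hyperglycaemic event is recorded (8.4). Patient and physician together influence insulin dose, and SAP 6.3.5 uses the mean dose over only the 3 days before each of the later visits. All of these can shift once allocation is known. The SAP's reassurance concerns error rates; it does not address bias in data still to be collected.

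At stake is how the Day 180 to Day 360 contrast with placebo is read, in a study meant to inform the design of later ones.

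**Working it through.** The documents give no figure for this, so the check is a comparison of texts plus date arithmetic.

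**Who is unblinded.** Protocol 5.10 attaches the 6-month limit to named parties that include sites and patients. The sentences on unblinding, there and in 10.8, name no recipient. No text in either document restricts the codes to an analysis team.

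**What the interim outputs would show.** SAP 6.9 plans the third interim with the final set of outputs where possible. SAP 6.3.3 sorts listings by treatment group and patient number, and SAP 7.2 includes a listing of treatment allocation for all subjects. The planned output therefore contains patient-level allocation; its distribution is not stated.

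**Whether the analysis separates later data.** SAP 6.3.8 tabulates TEAEs in total and for the AG019 treatment period. SAP 6.3.9 splits hypoglycaemia into before, during and after treatment. Neither has a cut at unblinding.

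**Inputs for the arithmetic**
- Trigger at Day 180 of the last patient needed (Protocol 5.10, 10.8); follow-up to Day 360 (5.2.2).
- Randomised patients: 10 per combination cohort, 4:1 (5.9). 2 x 10 = 20, of whom 16 active and 4 placebo, so 2 placebo per cohort.
- Post-baseline HbA1c at Days 56, 90, 180, 270, 360; post-baseline MMTT at Days 90, 180, 360 (7.3.3 and 7.3.4).

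**Formula.** A patient who started t days before the last patient needed for the trigger is unblinded at own Day 180 + t, leaving max(0, 180 - t) of 360 days after unblinding. Accrual is not given, so t is an assumption shown over a range:

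| t (days) | Days after unblinding | Share of 360 | Visits after unblinding |
|---|---|---|---|
| 0 | 180 | 50.0% | 270 and 360 |
| 30 | 150 | 41.7% | 270 and 360 |
| 60 | 120 | 33.3% | 270 and 360 |
| 90 | 90 | 25.0% | 360 (Day 270 falls on the trigger) |
| 120 | 60 | 16.7% | 360 |
| 150 | 30 | 8.3% | 360 |
| 180 or more | 0 | 0% | none |

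The ceiling is therefore 180 days, 2 of 5 HbA1c visits and 1 of 3 MMTTs.

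**IDAA1c.** IDAA1c = HbA1c (%) + 4 x dose (U/kg/24h). The documents give no size for a dose shift caused by knowing the allocation. As an illustration only, 0.05, 0.1 and 0.2 U/kg/24h give 4 x 0.05 = 0.2, 4 x 0.1 = 0.4 and 4 x 0.2 = 0.8 units.

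**Primary endpoint.** Under each trigger, every randomised patient being unblinded has already passed Day 180, so TEAEs to 6 months are collected before the break.

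**The case against.** The strongest reply is that the documents do not say sites and patients will be told. The unblinding sentence is passive and tied to analysis. The same section says, without a time limit, that codes should not be broken outside a medical emergency. Code access is governed by an IRT manual and the second interim by an Interim Analysis Plan, neither of which is available here. This stands as a limit on certainty. It does not remove the gap: the emergency rule concerns individual code breaks, and the expiry of the blind is written against sites and patients by name.

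Second, 180 days is a worst case. Under 5.10 the ceiling applies to the last patient across both cohorts. Under 10.8, Combination Cohort 1 also waits for two Combination Cohort 2 patients; if they start after the last Cohort 1 patient, no Cohort 1 patient reaches 180 days. Time spent on data decisions before the break shortens the window further. All of this stands.

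Third, the affected data carry limited weight. The study is descriptive, no formal comparison is planned, and each cohort has 2 placebo patients. HbA1c and C-peptide are central-laboratory assays. Day 180 is 124 days after the last AG019 dose (180 - 56) and 168 days after the last planned infusion (180 - 12). SAP Table 1 also has no separate row for the two open-label patients in each cohort, so the active group is never wholly blinded. These points lower the priority. They do not justify leaving the point unstated, because with 2 placebo patients one changed judgement visibly alters a descriptive table.

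Fourth, SAP 6.9 reports that the second interim has been done. By the 10.8 schedule that was the Combination Cohort 1 unblinding, so restricting codes may come too late for that cohort. This also stands and shapes the fix.

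**Conclusion.** The concern holds as a gap in the plan: the blind on sites and patients lapses at the Day 180 analyses, code recipients are not limited, and later judgement-dependent secondary data are not separated from blinded data. It is worth correcting but does not threaten the study's main result.

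A reader might infer three stronger things that the documents do not support:
- **That sites and patients are certainly told their allocation.** No recipient is named; this is a strong inference from the 6-month limit.
- **That half of every randomised patient's follow-up is open-label.** That is the ceiling for the last patient needed for the trigger. The share falls to zero for anyone who started 180 or more days earlier, and how many of the 20 are affected cannot be determined.
- **That the primary endpoint or an error rate is compromised.** Primary data precede the break, and there are no tests.

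The exposed items are adverse event reporting and relatedness, insulin dose and hence IDAA1c, and hypoglycaemia reports. The HbA1c and C-peptide assays are less exposed, although insulin management could still influence them. The sizes assume nominal visit days and release of the codes at the trigger.

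**What to change.** - **Protocol 5.10 and 10.8:** state that allocation at the interims goes only to a named analysis team. Keep sites, patients and site-facing sponsor and CRO staff blinded until the last Day 360 visit wherever the blind is still intact, with emergency unblinding unchanged. Outputs leaving that team before then should be aggregate only, without patient-level listings by arm. Reconcile the three statements of the unblinding trigger at the same time.
- **Patients already unblinded (probably Combination Cohort 1):** record each unblinding date. Present later adverse event, insulin and IDAA1c, and hypoglycaemia data separately, labelled open-label.
- **SAP 6.9:** qualify the sentence on the influence of the interims so that it covers error rates only, not bias in data collected after unblinding.

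The cost is wording in both documents, a change to IRT access rights and one extra split in the affected tables. Site-facing sponsor staff would wait longer for patient-level allocations.
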